# SAP Read-Out for October 28, 2021

**Date created: November 4, 2021**

## Introduction

This document describes the detail of the analysis read-out for the October 28, 2021 dataset. This document is an appendix to the Statistical Analysis Plan for the “UPMC Antibody Treatment and Evaluation Center”, and is a follow-up to the read-out for September 30, 2021, now that the trial population of interest (July 14 to September 29, 2021) has passed 28 day follow-up.

The September 30, 2021 read-out was conducted early, prior to all patients having reached 28 day follow-up, due to the Delta variant crisis.

- We will analyze and report two treatment arms (below).
- Unblinded data from this analysis can be shared with investigators, to prepare the public report. This unblinding is appropriate as there are no “control” arms as all patients receive mAB treatment, and the urgency of Delta.
  - Results from the primary analysis can be released first to investigators before sensitivity and subgroup analyses are complete.
- UPMC continues to provide treatment with all available mAbs, with randomization allocation.

## Treatment Arms

There are two treatment arms that will be included in this analysis. The arms are:

1. C+I (casirivimab and imdevimab)
2. S (sotrovimab)

B+E (bamlanivimab and etesevimab) became available again at UPMC on September 16, 2021, due to a U.S. Government decision. However, only a small amount of patients received B+E from September 16 to September 29, 2021, relative to the much larger number that received C+I or S for the trial period of interest. Therefore, we have little belief a strong statistical conclusion for B+E exists. In addition, we continue to randomize into B+E. For these reasons, we will not analyze B+E in this readout.

## Primary Endpoint

The primary endpoint for this read-out is hospital-free days at day 28.

## Primary Analysis Population

The primary analysis population for this read-out is the “As-Infused” population. This analysis will include all patients infused with a randomized mAb allocation in an ED or infusion center from July 14, 2021 until September 29, 2021. The date of the data set snapshot is on October 28, 2021. This analysis will not include any patients infused before July 14, 2021.

Due to mAb shortages, the below two situations arose and will be analyzed as follows:

### **1. No therapeutic interchange possible (InterChangeIndic)**

Due to episodic mAb shortages, some patients were treated at sites with only 1 available mAb at the time of treatment. However, prescribing physicians and patients were unaware of drug availability at time of randomization, a patient could be randomized to a different mAb on the same day and city (just with different availability by site), and bias is unlikely in the patient types or clinical management during the times when only 1 mAb was available at a given site.

Therefore, these patients will be included in the primary analysis. This variable will be included in the dataset for this readout and will be used in a sensitivity analysis where these patients will be excluded (page 4).

### **2. Not IV route (SUBQ\_FLAG)**

To increase treatment capacity, UPMC began SQ (subcutaneous) C+I injections starting in mid-September as more SQ treatments can be done per day than IV. We sought to compare mAbs given via the same route (IV) and the primary analysis population is the “As-Infused” population.

Therefore, these patients will be excluded from the primary analysis. This variable will be included in the dataset for this readout, for only descriptive purposes.

## **Primary Analysis Model**

The primary analysis model is as described in the trial SAP.

The primary analysis for the primary endpoint is a cumulative proportional odds model. Let the probability of an outcome of less than or equal to  $y$  be  $\pi_y = Pr(Y \leq y)$ . Let  $a$  be the indicator of treatment arm ( $a=1,\dots,k$ ). The model adjusts for the following baseline variables:

6. ED or infusion center (0=infusion center, 1=ED)
7. Age (with categories of <30, 30-39, 40-49, 50-59, 60-69, 70-79, and  $\geq 80$ ; 60-69 will be used as the referent)
8. Sex (sex at birth, male is the referent)
9. Covid variant is not modeled in this primary analysis, as the vast majority of all variants measured at UPMC and in state-wide GSAID data have been Delta for this readout's time period.
10. Time (two-week epochs of time are used for adjustments; the most current 4-week period is the referent)

The primary analysis model is based on a cumulative logistic regression, where  $\pi_y = Pr(Y \leq y)$ , where

$$\log\left(\frac{\pi_y}{1-\pi_y}\right) = \alpha_y - \theta_a \delta_{[a]} - \sum_{v=1}^4 \beta_{vj} \delta_{vj} - \lambda_{[time]}; \quad y = -1, 0, 1, 2, \dots, 27.$$

The additive covariate effects across all treatment arms for each patient are modeled through the  $\beta$  parameters. The  $\delta$  parameters are indicator functions for the treatment arm and covariate values for the baseline covariates. The efficacy of the treatment arms is modeled with the  $\theta$  parameters. The

ordinal effect parameters ( $\alpha_y$ ) are modeled with a Dirichlet distribution with equal weight on each outcome and a sum of 1.

The baseline covariate effects are modeled with independent weak prior distributions:

$$\beta_{vj} \sim N(0, 10^2), v = 1, \dots, 4; j = 1, \dots, n_v.$$

The appropriate coefficients will be set to 0 within each covariate for identifiability (the goal will be the largest category set to 0).

The effects of time are adjusted within the model using two-week epochs and a smoothing model over time. The modeling of the time effects is set up with the most current period (2 epochs combined being the most recent month are set to 0):

$$\lambda_1 \equiv \lambda_2 \equiv 0$$

$$\lambda_2 - \lambda_1 \sim N(0, 0.15^2)$$

$$\lambda_T - 2\lambda_{T-1} + \lambda_{T-2} \sim N(0, \tau_\lambda^2); T \geq 3$$

$$\tau_\lambda^2 \sim IG(0.25, 0.00562)$$

The prior distributions for the mAB treatment effects are weak:

$$\theta_a \sim N(0, 10), a = 1, 2.$$

The treatment arm with the largest sample size should be selected as the referent arm (label a=1) for treatment effects and assigned a treatment effect of  $\theta_1 = 0$ .

### Model Convergence

Given the complexity of the model, conventions may be taken by the analysis team if there are convergence issues or model stability issues. For example, there may be outcome categories in the 30 possible primary outcome values (e.g., k number of hospital-free days, patient death) that do not occur. If this happens at analysis, the cells will be combined to achieve model convergence. For example, if the 4 hospital-free day outcome value does not occur it will be combined with 3, and so on, until every cell has occurred. Additional model stability conventions will be taken to preserve the model stability.

### Missing and Partial Data

If there are missing covariates for a patient in the as-infused patient population, the following conventions will be used.

3. If the treatment arm is missing the patient will be ignored.
4. If a baseline covariate is missing the referent value for that covariate will be used

For all model analyses, only patients who have achieved 28-days of follow-up from the date of the index infusion will be used in the primary analysis. No use or imputation of patient data for patients with less than 28 days will be conducted.

Given the EHR-based data summaries there will be no missing outcome data, barring patients who received treatment less than 28 days ago. If there is deemed to be a corrupted outcome that patient will

be ignored. Some patients may have 28 hospitalization-free days that at subsequent analyses are found to have out of system hospitalizations. The data will be updated at future analyses.

### Sensitivity Analyses

We will conduct the following sensitivity analysis:

- Exclude the no therapeutic interchange possible patients (InterChangeIndic)

## Subgroup Analyses

For subgroup analyses the model is fit independently in each subgroup classification. If the subgroup is a covariate in the model that covariate is removed from the analysis.

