### **Modeling Treatment Heterogeneity**

During the course of the trial, and during a trial read-out, inferences of relative treatment effect by different subgroups may be utilized. In these cases, the treatment effect is modeled as a function of subgroup within the single larger model. Each level of the subgroup will be identified and added as a covariate in the model and then the treatment effect,  $\theta_{as}$ , will be modeled separately within each subgroup,  $s = 1, \dots, S$ , as  $\theta_{a1}, \theta_{a2}, \dots, \theta_{aS}$ , with hierarchical prior distribution:

$$\theta_{as} \sim N(\mu_a, \tau_a^2), a = 1, \dots, k; s = 1, \dots, S.$$

$$\mu_a \sim N(0, 10^2); \tau_a^2 \sim IG(0.25, 0.1).$$

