### 1. A priori, per approved protocol

- By vaccine status (fully, partially, unvaccinated, unknown)

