## Specific Analyses

---

#	Status	Population	Endpoint	Other
1	Primary	As-Infused to C+I or S from July 14, 2021 until September 29, 2021	HFD	Sensitivity and subgroup analyses will also be conducted as detailed above.

---

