### Graphical summaries:

1. Stacked bar plots and cumulative distributions of HFDs by treatment arm
2. Stacked bar plots and cumulative distributions of HFDs by location
3. Stacked bar plots and cumulative distributions of HFDs by vaccine status
4. Stacked bar plots and cumulative distributions of HFDs by symptom onset

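### October read-out: each vaccine-status level is fitted separately and no comparison between levels is planned, so the plan does not directly address whether the C+I v S effect differs by vaccine status

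*SAP*

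**What the plan says.** **Main SAP, Modeling Treatment Heterogeneity.** The section covers read-outs: "During the course of the trial, and during a trial read-out, inferences of relative treatment effect by different subgroups may be utilized". When that is done, "the treatment effect is modeled as a function of subgroup within the single larger model", and "Each level of the subgroup will be identified and added as a covariate in the model". The level-specific effects share a hierarchical prior, theta_as ~ N(mu_a, tau_a^2), with tau_a^2 ~ IG(0.25, 0.1). No contrast between levels is named.

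**Appendix for the October 28, 2021 read-out, Subgroup Analyses.** "For subgroup analyses the model is fit independently in each subgroup classification". It adds: "If the subgroup is a covariate in the model that covariate is removed from the analysis". It does not mention the hierarchical model. Vaccine status, with four levels including unknown, is the only entry under the a priori heading. Symptom onset and location are labelled post hoc.

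**Planned output in the same appendix.** The Specific Analyses table says: "Sensitivity and subgroup analyses will also be conducted as detailed above". The tables of posterior probabilities and odds ratios are for the primary analysis. The only listed output by vaccine status is "Stacked bar plots and cumulative distributions of HFDs by vaccine status".

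**Protocol.** The Objectives section (6) hypothesises that effects differ between antibodies, by variant and by patient characteristics. The Statistical Analysis section (24) says the SAP will consider such heterogeneity. The Strata section (22) includes prior vaccination.

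**The concern.** A subgroup analysis is meant to show whether the treatment effect differs between levels. Separate fits answer another question, namely what the effect is within each level. Unless the levels are compared, the reader sees four odds ratios whose precision depends on level size. The natural shortcut is to note that one interval excludes 1 and another does not, and to call that a difference. A large and a small level with the same true effect will often produce this pattern.

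The listed plot does not help. Hospital-free days by vaccine status, with arms combined, show prognosis by status and not a difference in treatment effect.

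There is also a smaller documentation gap. The main SAP prescribes one model for read-out subgroups and the appendix uses another, without saying that it departs or why. The appendix's Introduction allows primary results to reach investigators before the subgroup work is complete, so the governing method is best settled in writing beforehand.

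**Working it through.** **Step 1: the two subgroup methods compared.**

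| | Main SAP | October appendix |
|---|---|---|
| Fit | one joint model | one fit per level |
| Level effects | shared hierarchical prior | no sharing |
| Contrast between levels | none named | none named |
| Statement on which governs | none | none |

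Following the main SAP would therefore settle the documentation gap but would not supply the missing comparison.

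**Step 2: inputs.** The documents give no sample size, event rate, arm split, vaccine shares or effect for this read-out, so there is no plan figure to reproduce and every size below is an assumption. Base case: N = 3,500; p = 12% with HFD below 28; arm share r = 0.30; shares fully/partially/unvaccinated/unknown 30/8/45/17%. The full grid has 24 scenarios: N 2,000 or 3,500; p 12 or 20%; split 30:70 or 50:50; shares as above, 40/4/46/10% or 25/15/35/25%.

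**Step 3: precision within a level** (normal approximation, outcome split at 28 days, no covariates).

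SE = sqrt[1/(n r p(1-p)) + 1/(n(1-r) p(1-p))]

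Fully vaccinated, n = 0.30 x 3,500 = 1,050: sqrt[1/(1,050 x 0.3 x 0.1056) + 1/(1,050 x 0.7 x 0.1056)] = sqrt(0.0301 + 0.0129) = 0.21. The other levels give 0.40, 0.17 and 0.28.

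**Step 4: chance of a mixed picture when nothing differs.** For a common log odds ratio t, a level's 95% interval excludes 1 with probability w = Phi(t/SE - 1.96) + Phi(-t/SE - 1.96). Some intervals exclude 1 and others do not with probability 1 - prod(w) - prod(1-w). At OR 1.22 the four w are 0.160, 0.079, 0.217 and 0.112. The result is 1 - 0.0003 - (0.840 x 0.921 x 0.783 x 0.888) = 1 - 0.0003 - 0.538 = 0.46.

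| Common true OR | Mixed picture, base case |
|---|---|
| 1.00 | 18.5% |
| 1.05 | 20% |
| 1.11 | 27% |
| 1.22 | 46% |
| 1.35 | 71% |

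The first row is ordinary multiplicity: 1 - 0.95^4 = 18.5%. At OR 1.22 the 24 scenarios run from 35 to 64%.

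**Step 5: one named contrast.** Each patient belongs to one vaccine level, so separate fits are on different patients and the log ratio of odds ratios is a difference of independent estimates. Fully v unvaccinated, using unrounded SEs: SE = sqrt(0.207^2 + 0.169^2) = 0.268. If the true effects are equal, its 95% interval excludes 1 in about 5%, whatever the common OR. Its precision is limited: exp(1.96 x 0.268) = 1.69, so the interval spans a factor of about 1.7 either side. A true ratio of 1.65 (log 0.5) is detected with probability Phi(0.5/0.268 - 1.96) = 46%. Across the grid the factor is 1.43 to 2.16 and detection 25 to 78%.

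**Step 6: would the hierarchical model alone solve it?** Simulation with the main SAP's prior, at OR 1.22, gives a mixed picture in 41% of base-case read-outs, against 47% for separate fits (8,000 replicates). Across the grid it removes only 2 to 8 points. It lowers detection of an effect confined to the smallest level (log OR 0.7) from about 42% to 22% in the base case. The joint model matters more if all six vaccine pairs are shown: with equal true effects, at least one pair excludes 1 in 19 to 22% with separate fits and 5 to 11% with the hierarchical model.

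**The case against.** **The method is not really in doubt.** The appendix is later, specific to this dataset, and gives one definite subgroup method. An analyst would know what to run. This stands. A reader might infer that two live methods contradict each other, but the text supports only an undeclared departure.

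**Dropping the subgroup covariate is not a second conflict.** Within a level the subgroup variable is constant, so it must drop out. Vaccine status is not in the primary model anyway; of the three October subgroups the sentence touches only location. This stands.

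**July is no precedent for a contrast.** The July read-out listed arm effects for each calendar epoch and a plot by arm and epoch, but no between-epoch contrast. This stands. July supports splitting the plot by arm, not the contrast.

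**No passage promises a contrast, and it could be worked out from the level-specific estimates.** True, if those estimates are reported; the commitment to do the subgroup analyses suggests they would be. But a contrast chosen after seeing four estimates is not a pre-named one, and the protocol's hypothesis concerns differences between patients.

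**The harm is a possible misreading.** No decision rule in the plan uses whether a subgroup interval excludes 1. This stands and limits the severity.

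**The size depends on the assumed effect.** The 35 to 64% range holds the common OR at 1.22 and is not an uncertainty range. Near equivalence the figure falls towards 18.5%; with a larger common effect it rises.

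**Conclusion.** The point holds at low severity. The October appendix plans separate fits by vaccine status and no comparison between levels, so its listed outputs do not directly show whether the C+I v S effect differs by the one subgroup it calls a priori. With equal true effects, the assumed base case gives a misleading mixed picture in 18.5% to 71% of read-outs as the common OR goes from 1.00 to 1.35, against about 5% for one named contrast. These figures rest on assumed sizes and a normal approximation; they illustrate the mechanism and do not predict this trial's result.

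Two stronger readings are not supported. A reader might infer that separate fits are wrong and the hierarchical model is required. The choice is a trade-off, and changing the model alone barely reduces the mixed picture. A reader might also infer that the trial's conclusions are at risk. The inferiority and equivalence triggers and the primary C+I v S result do not depend on these subgroup fits.

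**What to change.** 1. **Subgroup Analyses (October appendix).** Add for vaccine status one pre-named ratio of odds ratios with a 95% credible interval, obtained by differencing posterior draws from the two separate fits. Possible wording: *The difference in treatment effect by vaccine status will be summarised by the ratio of the S v C+I odds ratio in fully vaccinated to that in unvaccinated patients, with a 95% credible interval. Level-specific intervals will not be compared by whether each excludes 1, and a contrast interval that includes 1 will not be taken as evidence of no heterogeneity.* Fully v unvaccinated is an example; the sponsor should name the pair.
2. **Graphical summaries.** Split the vaccine-status plot by arm.
3. **Governing section.** State that the appendix replaces Modeling Treatment Heterogeneity for this read-out, or the reverse, with a reason. If all vaccine pairs are shown, take them from the hierarchical model.

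Contrasts for the two post hoc factors and a second, hierarchical analysis are optional. If both models are reported, name the main one, since they can disagree.

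**Cost.** A few sentences, one table row and one redrawn plot. Vaccination status is already in the listed dataset and the contrast needs no further fit. Showing all pairs would need one extra fit of a model already specified. The drawback is imprecision: a 95% interval spanning a factor of about 1.7 either side in the base case.

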### 1. A priori, per approved protocol

- By vaccine status (fully, partially, unvaccinated, unknown)

### 2. Post hoc subgroup analyses

- By symptom onset (>5 days or  $\leq 5$  days)
- By location (0=infusion center, 1=ED)

### Trial Inferences

For the primary analysis, there is no “control” treatment and so all inferences are made comparing the individual treatment arms to each other. The main quantity of interest will be the relative odds ratio between any two treatments arms

$$OR_{ij} = \exp(\theta_i)/\exp(\theta_j).$$

The posterior probability that the odds ratio for arm  $i$  compared to arm  $j$  is greater than 1 (signifying that treatment  $i$  is superior to treatment  $j$ ) is used as a comparison between arms. Additionally, the posterior mean and 95% confidence interval between arms will be used to summarize relative treatment effects.

**Arm Inferiority:** If one of the arms has a 99% chance of being inferior to any of the other available arms then the inferior arm will be declared inferior and may be removed from the trial. There may be conditions of the pandemic (variation frequency, new variations) or drug supply concerns that an arm is retained.

**Equivalence:** Any two arms in the trial may reach a declaration of equivalence. It is anticipated that no actions would take when equivalence is reached but a declaration and public disclosure may be made. There is a sliding scale of equivalence with different levels of equivalence bounds. A declaration of equivalence will be tied to the equivalence level. Equivalence with a bound of  $d$  is declared if the posterior probability of the odds ratio is with  $d$  is at least 95%:

$$\Pr\left(\frac{1}{1 + \delta} \leq OR_{ij} \leq 1 + \delta\right) \geq 0.95$$

The following levels are pre-defined:

6. The first level of equivalence occurs when there is 95% posterior probability that the odds-ratio is within a bound of d=0.25
7. The second level of equivalence occurs when there is a 95% posterior probability that the odds-ratio is within a bound of d=0.20
8. The third level of equivalence occurs when there is a 95% posterior probability that the odds-ratio is within a bound of d=0.15
9. The fourth level of equivalence occurs when there is a 95% posterior probability that the odds-ratio is within a bound of d=0.10
10. The fifth level of equivalence occurs when there is a 95% posterior probability that the odds-ratio is within a bound of d=0.05

## Dataset

- Pitt Data Freeze on 10/28/2021
- 2 treatment arms for primary analysis
  - C+I (casirivimab-imdevimab)
  - S (sotrovimab)
- Include patients infused from 0:00a July 14, 2021 until September 29, 11:59p
  - No patients from before July 14, 2021
- No patients who received treatment less than 28 days ago
- Included for descriptive purposes (not for primary analysis)
  - Patients who received SQ (subcutaneous) injections
  - Patients who received B+E (bamlanivimab and etesevimab)
- **InterChangeIndic**
- **Vaccination Status**
- **Symptom Onset Date**
- **SUBQ\_FLAG**
- **ReasonNotInfused**
  - Admitted
  - Declined
  - Ineligible
  - Infusion Incomplete
  - Pending return call
  - Scheduled
  - Unable to contact
  - Unable to travel

---

## Specific Analyses

---

#	Status	Population	Endpoint	Other
1	Primary	As-Infused to C+I or S from July 14, 2021 until September 29, 2021	HFD	Sensitivity and subgroup analyses will also be conducted as detailed above.

---

### 1. Primary Analysis

---

The following posterior probabilities will be reported:

Quantity of Interest	Posterior Probability
C+I inferior to S	
S equivalent to C+I (as per the pre-defined 5 levels and associated bounds)	
S inferior to C+I	

---

### Statistical Triggers Met for Equivalence with delta ranges of equivalence

---

The following will be reported:

Odds-Ratio Parameter	Mean	SD	Median	95% Credible Interval
Age < 30				
Age 30 – 39				
Age 40 – 49				
Age 50 – 59				
Age 60 – 69	1			
Age 70 – 79				
Age 80+				
Female				
Time Bucket 1				
...				
Time Bucket k-1				
Referent Arm	1			
Arm #2				

---

### Graphical summaries:

1. Stacked bar plots and cumulative distributions of HFDs by treatment arm
2. Stacked bar plots and cumulative distributions of HFDs by location
3. Stacked bar plots and cumulative distributions of HFDs by vaccine status
4. Stacked bar plots and cumulative distributions of HFDs by symptom onset

